7.1.1.2 Sample Size Determination

We will enroll approximately 60 subjects in up to 4 study centers in the US. This study is a feasibility trial and no sample size calculations are required.

7.1.1.3 Missing Data

Missing data will be reported at each visit for each outcome. No imputations will be performed for missing data.

7.2 Justification of Clinical Investigation Design

This is a prospective, open label, multicenter feasibility trial to evaluate the therapeutic efficacy of different BurstDR[™] microdosing patterns in patients with chronic intractable pain. Use of these new energy efficient stimulation parameters has the potential to prolong the battery life of a non-rechargeable, primary cell Implantable Pulse Generator (IPG). It also has the potential to improve patient convenience by decreasing the frequency with which the patient has to recharge a non-primary cell IPG. Thus, it is crucial to evaluate these potential energy efficient stimulation parameters in SCS eligible patients.

7.3 Multiplicity

All statistical tests will be performed with a type-1 error rate 0.05, unless otherwise stated. Family-wise error for RMANOVA will be addressed using Tukey's pairwise post-hoc comparisons.

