5.1 Clinical Investigation Design

This is a prospective, open label, multicenter feasibility trial to evaluate the therapeutic efficacy of different BurstDR[™] microdosing patterns in patients with chronic intractable pain.

[figure not shown]
Subjects diagnosed with chronic intractable back and/or leg pain, with no prior history of SCS therapy, will be considered for inclusion in this study. After baseline evaluation, subjects will undergo a SCS trial using the Abbott Invisible Trial system. During the trial implant phase, SCS leads will be implanted in the dorsal column based on physician discretion. According to standard clinical practices performed in the United States (US), the trial phase will last around 3-7 days. At the start of the trial phase, patients will be

programmed with the first ON/OFF stimulation pattern (30 second STIM ON, 90 seconds STIM OFF). Patients who do not achieve adequate pain relief (at least 50% reduction in back and/or leg VAS from baseline) within the first 3-4 days will be reprogrammed to a new ON/OFF stimulation pattern (5 seconds ON/ 15 seconds OFF). Patients, who still do not achieve adequate pain relief within 2 to 3 days from reprogramming, will be reprogrammed to a continuous mode of BurstDR[™] stimulation and their trial evaluation will continue. These patients will be evaluated for an additional 2 days. At the end of the SCS trial, all subjects that experience at least 50% pain relief (according to average back and/or leg VAS) using one of the two microdosing burst stimulation paradigms will be considered further participation in the study. See Figure 1.

Patients who have passed the trial phase and have received permanent implantation will be programmed based on the stimulation mode used for their trial success. Pain intensity, quality of life, disability, anxiety, depression, pain catastrophizing, satisfaction, and medication usage will be assessed at baseline, after SCS trial and at the 1, 3 and 6 month follow up. Adverse events will be collected throughout the study period.

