5.3.1 Primary Endpoint

• Evaluate the change in pain intensity between baseline, trial and long-term follow up evaluations using the Visual Analog Scale (VAS) assessments.

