7.1.1 Primary [Safety/Effectiveness] Endpoint Hypothesis(es)

7.1.1.1 Analysis Methodology

The primary analysis to assess improvement in pain intensity, using VAS, will be conducted using repeated measures ANOVA (RMANOVA). Post-hoc Tukey's pairwise comparisons will follow to determine specific differences between follow-up visits. Secondary analyses to assess improvements in quality of life, disability, anxiety, depression catastrophizing and satisfaction will be conducted using repeated measures ANOVA (RMANOVA) or the most appropriate statistical methods.

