7.4 Overall Sample Size

We will enroll up to 60 subjects.

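### No primary VAS contrast is named, the Tukey family is undefined, and the 0.05 family-wise rate is assured only under sphericity

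*Combined protocol and SAP*

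**What the plan says.** The primary endpoint in Section 5.3.1 is: "Evaluate the change in pain intensity between baseline, trial and long-term follow up evaluations using the Visual Analog Scale (VAS) assessments". It names no visit and no pair of visits.

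Section 7.1.1.1 gives the method: "The primary analysis to assess improvement in pain intensity, using VAS, will be conducted using repeated measures ANOVA (RMANOVA"). It continues: "Post-hoc Tukey's pairwise comparisons will follow to determine specific differences between follow-up visits". Section 7.3 sets the error rate, "All statistical tests will be performed with a type-1 error rate 0.05, unless otherwise stated", and makes Tukey the family-wise control: "Family-wise error for RMANOVA will be addressed using Tukey's pairwise post-hoc comparisons".

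Section 5.1 fixes the visits. VAS is among the outcomes that, with "medication usage will be assessed at baseline, after SCS trial and at the 1, 3 and 6 month follow up", give five time points. Section 7.4 says "We will enroll up to 60 subjects".

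Section 7 does not mention sphericity, an epsilon correction, a covariance structure, the error term for the pairwise tests, or a confidence interval. Section 7.1 says that formal hypothesis testing is not required, and Section 7.6 says that there are no formal success criteria.

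**The concern.** Three things are left open.

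- **The main result.** The primary objective is efficacy on pain. Change from baseline to the last visit is the natural summary, but neither it nor any other contrast is singled out.
- **The family.** The phrase "pairwise comparisons will follow to determine specific differences between follow-up visits" points to the 1, 3 and 6 month visits, which Section 6.4.6 calls follow-ups. That makes 3 pairs, none with baseline. The endpoint in Section 5.3.1 points to all five time points, which makes 10 pairs, 4 of them changes from baseline. The choice could be made after the data are seen.
- **The error term.** Tukey after RMANOVA is usually run on one pooled error term, which is valid when every pair of visits has the same difference variance (sphericity). The design works against that. Baseline VAS must be at least 6.0 cm, and only subjects with at least 50% relief in the trial phase continue. Follow-up VAS has no such limits.

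At stake are the stated 0.05 and the precision of the one estimate that a later study would most want. Section 7.1 says that the results may be used to generate such a study.

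**Working it through.** **Inputs from the documents.** Type I error 0.05 (sidedness not stated; taken as two-sided), five visits, up to 60 subjects. **Assumed.** A pooled error term; all SDs and correlations; the number of subjects with complete data (30, 40 and 60 used).

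**1. The stated 0.05.** The Tukey critical value is q(0.95; k, (n−1)(k−1)), applied to the pooled subject-by-visit mean square. Under sphericity the family-wise error is 0.05 by construction. Simulation with k = 5 and compound symmetry (40,000 runs per setting) gave 0.052, 0.050 and 0.049 at n = 60, 40 and 30. The plan's figure is reproduced under that condition.

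**2. Cost of an unnamed contrast.**

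- Five visits give 5×4/2 = 10 pairs. At n = 60, df = 59×4 = 236 and q = 3.888. The multiplier is 3.888/√2 = 2.749, a per-pair two-sided alpha of 0.0064.
- A single planned paired interval uses t(0.975; 59) = 2.001. The width ratio under sphericity is 2.749/2.001 = 1.37.
- At n = 30 the multipliers are 2.771 and 2.045, a ratio of 1.36.
- On the literal reading there are 3 pairs at about 0.019 each, and baseline to 6 months is not among them.

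**3. Is sphericity plausible?** If baseline VAS were spread evenly over 6 to 10 cm, its SD would be 4/√12 = 1.15 cm. Both selection rules were also simulated directly (40 completers, latent SDs 2.0 to 2.5, equal latent correlations 0.3 to 0.7). This left SDs of about 1.0 to 1.4 cm at baseline and end of trial, against 1.5 to 2.3 cm later. The largest pairwise difference SD was 1.5 to 1.9 times the smallest, and the family-wise error was 5.5 to 6.3%.

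**4. Direction of the error for baseline to 6 months.** Take SD 1.2 at baseline, 2.5 at the other four visits, and correlation 0.2 with baseline.

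- Variance of the baseline-to-6-month difference: 1.2² + 2.5² − 2×0.2×1.2×2.5 = 6.49, so SD 2.55.
- Variance of a difference between two later visits with correlation r: 2×2.5²×(1−r).
- The pooled error corresponds to the average over the 10 pairs.

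| r among later visits | later-pair variance | average of 10 pairs | pooled SD | pooled/true |
|---|---|---|---|---|
| 0.8 | 2.50 | (4×6.49 + 6×2.50)/10 = 4.10 | 2.02 | 0.79 |
| 0.6 | 5.00 | (4×6.49 + 6×5.00)/10 = 5.60 | 2.37 | 0.93 |
| 0.3 | 8.75 | (4×6.49 + 6×8.75)/10 = 7.85 | 2.80 | 1.10 |

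The pooled standard error is 21% too small in the first row and 10% too large in the last. Only the unknown correlation has changed.

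**5. Family-wise error and coverage under assumed covariances.**

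- All means equal, non-spherical: family-wise error 0.052 to 0.076.
- Baseline truly different: error among the remaining true nulls 0.003 to 0.050, so no material inflation.
- Tukey interval for baseline to 6 months at n = 60 (nominal 0.9936): coverage 0.969 to 0.990 where the pooled standard error is too small, and 0.997 in the reverse case (r = 0.3).
- Average Tukey width relative to the paired 95% interval: 1.10 to 1.29 in the former settings, 1.39 in the compound-symmetry simulation (1.37 by formula), and 1.53 in the reverse case.
- Paired 95% interval with its own standard error: coverage 0.948 to 0.952 in every setting.

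**The case against.** The strongest reply has four parts.

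- **Little depends on it.** The study is a feasibility study with no formal hypothesis, no sample size calculation and no success criterion. No decision rule turns on 5% against 7%. This stands and limits the weight of the point.
- **Tukey is conservative for the contrast of interest.** A reader might infer that the planned interval is wrong. The documents specify no interval, and the Tukey interval for baseline to 6 months covered above 95% in every setting tried. Its fault is unnecessary width and a level that depends on an unstated assumption.
- **The failure of 0.05 is conditional.** A reader might infer that the stated rate is not delivered, or that the design rules sphericity out. Neither is shown. The rate holds under sphericity, and difference variances depend on correlations that the documents do not give. The inflation is modest and appears when all five means are equal, an unlikely case given the entry and continuation rules. The pooled error term is a usual default, not a stated choice, and Section 7 allows further detail in a separate SAP.
- **Other contrasts matter.** Section 5.3.1 includes the trial phase, and Section 5.1 defines adequate relief after implant against relief in the trial. End-of-trial to follow-up comparisons are therefore relevant and should not be dismissed. This is accepted in the fix.

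What remains is that no primary contrast is named, the family can be read two ways, and the error term and sphericity are not addressed.

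**Conclusion.** The point holds in this limited form. The text alone shows that no primary VAS contrast is named and that the Tukey family is either 3 follow-up pairs without baseline or 10 pairs at about 0.0064 each. On the 10-pair reading, the baseline-to-6-month interval is about 37% wider than a planned paired 95% interval under sphericity, and 10 to 53% wider across the covariances tried.

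The rest is conditional on a pooled error term and on assumed SDs, correlations and completer numbers. The 0.05 rate is then assured only under sphericity, which the two selection rules make unlikely, and the family-wise error is about 5 to 8% when all means are equal. A reader might conclude that the pooled standard error always understates the baseline-to-6-month error. The documents do not support that, because the sign depends on correlations that they do not give. The consequence is modest, but the change is worth making because it costs only wording.

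**What to change.** In Sections 7.1.1.1 and 7.3:

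1. Name change in VAS from baseline to 6 months as the primary contrast. Report it with a 95% confidence interval from its own paired standard error, or from a mixed model with unstructured covariance.
2. Report the other three changes from baseline, and end of trial to follow-up if wanted, with contrast-specific standard errors and Holm-adjusted p-values. State that the family-wise claim applies to this listed set.
3. Give the remaining visit-to-visit differences descriptively, and remove the Tukey sentences.

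If the sponsor prefers to keep all 10 pairs, the text should say so and use pair-specific standard errors. Bonferroni paired t tests gave a family-wise error of 0.034 to 0.042 in the settings tried.

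The change needs no further subjects, visits or data. Its cost is that formal all-pairs testing among the follow-up visits is given up.

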7.4 Overall Sample Size

We will enroll up to 60 subjects.

7.5 Timing of Analysis

Interim analyses may be conducted after the end of trial visit.

7.6 Success Criteria

There are no formal success criteria. This is an observational study.

7.7 Interim Analysis

No formal interim analysis is planned for this study.

7.8 Statistical Criteria for Termination

There are no statistical criteria for termination of this clinical investigation.

7.9 Deviations from Statistical Plan

If any deviations from the original statistical plan occur, such deviations will be documented in the clinical study report or statistical report containing the analysis results.

8 Risks and Benefits

The risks associated with SCS can be found in the Instructions for Use. The study does not require any additional procedures over the standard of care. There are no additional risks introduced to study subjects.

8.1 Risks Associated with the Device Under Investigation

We do not foresee any additional risk, beyond those normally associated with SCS therapy, described below.

8.1.1 Anticipated Adverse Device Effects

In addition to those risks commonly associated with surgery, the following risks are associated with implanting or using this neurostimulation system for SCS:

- Undesirable changes in stimulation, which may be related to cellular changes in tissue around the electrodes, changes in electrode position, loose electrical connections, or lead failure
- Lead migration, causing changes in stimulation and/or reduced pain relief
- Epidural hemorrhage, hematoma, infection, spinal cord compression, or paralysis from placement of a lead in the epidural space
- Cerebrospinal fluid (CSF) leakage
- Paralysis, weakness, clumsiness, numbness, or pain below the level of the implant
- Persistent pain at the electrode or IPG site
- Seroma (mass or swelling) at the IPG site
- Infection of the lead extension at the exit zone during trial or infection of the IPG site
- Allergic or rejection response to implant materials
- Implant migration or skin erosion around the implant
- Anticipated adverse device effects
- Battery failure

These adverse events and adverse device effects are not specific to the study, but related to the approved SCS implant procedure.

8.1.2 Risks Associated with Clinical Investigation Assessments

There are no additional risks associated with the clinical investigation assessments beyond standard of care.

8.2 Risk Control Measures

Every possible effort will be taken to minimize the risks, including:

- Careful selection of experienced Investigators for the clinical investigation
- Adequate monitoring for each clinical investigation site
- Conducting the clinical investigation in accordance with the CIP, all applicable laws and regulations and any conditions of approval imposed by the appropriate IRB/EC or applicable regulatory authorities where the clinical investigation is performed
- Preparation of the SCS device and performance SCS implant procedure in accordance with the device IFUs
- Training of Investigators on the CIP

8.3 **Possible interactions with concomitant treatments**

There are no possible interactions with concomitant medical treatment and/or concurrent medical intervention beyond those associated with standard medical care using SCS.

8.4 Anticipated Benefits

There are no additional clinical benefits associated with the participation in this study beyond those anticipated with standard clinical SCS

8.5 Risk-to-Benefit Rationale

There are no additional risk-to-benefits associated with the participation in this study beyond those anticipated with standard clinical SCS.

9 Requirements for Investigator Records and Reports

9.1 Deviations from CIP

A deviation is defined as an instance(s) of failure to follow, intentionally or unintentionally, the requirements of the CIP. The investigator should not deviate from the CIP.

In some cases, failure to comply with the CIP may be considered failure to protect the rights, safety and well-being of subjects; such non-compliance exposes subjects to unreasonable risks. Examples: failure to adhere to the inclusion/exclusion criteria, failure to perform safety assessments intended to detect adverse events. Investigators should seek to minimize such risks by adhering to the CIP.

The PI must maintain accurate, complete, and current records, including documents showing the date of and reason for each deviation from the CIP. Relevant information for each deviation will be documented as soon as possible on the applicable CRF. The site will submit the CRF to the Sponsor.

The PI is required to adhere to local regulatory requirements for reporting deviations to IRB/EC.

Under emergency circumstances, deviations from the CIP to protect the rights, safety and well-being of subjects may proceed without prior approval of the Sponsor and the IRB/EC. Such deviations shall be documented and reported to the Sponsor and the IRB/EC as soon as possible.

9.2 Safety Reporting

Safety surveillance within this study and the safety reporting performed both by the investigator and Sponsor starts as soon as the procedure begins. This is defined as from the time the [dilator/device delivery system has been introduced into the body.

The safety surveillance and the safety reporting will continue until the last investigational visit has been performed, the subject is deceased, the subject/investigator concludes his participation into the clinical investigation or the subject withdrawal from the clinical investigation.

All adverse event data including deaths and device deficiency data (if applicable) will be collected throughout the clinical investigation and will be reported to the Sponsor on a CRF.

Adverse events will be monitored until they are adequately resolved or the subject has ended his/her participation in the trial, whichever comes first. The status of the subject's condition should be documented at each visit.

The investigator will report the event to the IRB/EC per their reporting requirements.

Reportable events to sponsor are considered:

- All Adverse Device Effects
- All Serious Adverse Events (whether or not the event is considered device or procedure related and regardless the randomization group)
- (if applicable) device deficiencies, that could have led to a serious adverse device effect
 - if either suitable action had not been taken;
 - if intervention had not been made or
 - if circumstances had been less fortunate

All events mentioned above will be reported to the Sponsor, as soon as possible, but no later than 72 hours of first learning of the event.

Reportable events shall be submitted to the Sponsor. The Sponsor will ensure that all applicable events and device deficiencies are reported to the relevant authorities as per regulations. The sites should notify the Sponsor of reportable adverse events.. Additional information may be requested by the Sponsor in order to support the reporting of AEs to regulatory authorities. The investigator must notify the IRB/EC, if appropriate, in accordance with national and local laws and regulations, of the AEs reported to the Sponsor. All adverse events will be reported as per applicable regulatory requirements.

9.2.1 Subject Death

All subject deaths are to be documented and reported to the sponsor within 72 hours after becoming aware of the event.

All subjects' deaths should be documented using the "Death Form" and a "Withdrawal Form".

9.2.2 Complaints

During the study, the investigator will be responsible for reporting all complaints. A complaint is defined as any written, electronic or oral communication that alleges deficiencies related to the identity, quality, durability, reliability, safety, effectiveness or performance of a device after it is released for distribution.

If the complaint involves an AE, the investigator must complete an AE CRF, including the information on the complaint and submit to Abbott as soon as possible.

Should a subject death be caused by the Abbott device or the device contributed to the death, the investigator should complete a Form 3500A (MedWatch) and submit to Abbott and the FDA within 10 days after becoming aware of the event.

9.3 Source records

Source documents will be created and maintained by the investigational site team throughout the clinical investigation. The data reported on the CRFs will be derived from, and be consistent with, these source documents, and any discrepancies will be explained in writing.

The following data can be recorded directly in the CRFs:

- Pain VAS scores
- EQ-5D scores
- ODI scores
- HADS scores
- PCS scores
- PGIC scores
- Medication usage form
- Programming form
- Adverse events form

9.4 Records Retention

The Sponsor and the Principal Investigators will maintain the clinical investigation documents as required. Measures will be taken to prevent accidental or premature destruction of these documents. The Principal Investigator or the Sponsor may transfer custody of records to another person/party and document the transfer at the investigational site or the Sponsor's facility, as appropriate.

These documents must be retained by the investigational site for a period of 2 years after the conclusion of the clinical investigation and made available for monitoring or auditing by the Sponsor's representative or representatives of the applicable regulatory agencies.

All original source documents must be stored for the maximum time required by the regulations at the hospital, research institute, or practice in question. If original source documents can no longer be maintained at the site, the investigator will notify the Sponsor.

10 Clinical Data Handling

The Sponsor will be responsible for the data handling. The Sponsor and/or its affiliates will be responsible for compiling and submitting all required reports to governmental agencies. Data will be analyzed by the Sponsor and may be transferred to the Sponsor's locations worldwide and/or any other worldwide regulatory authority in support of a market-approval application.

During this study the following documents will be produced:

- Patient's ICF
- Enrollment case report form
- Inclusion/Exclusion case report form
- VAS case report form
- EQ-5D case report form
- ODI case report form
- HADS case report form
- PCS case report form
- PGIC case report form

- Medication usage form
- Programming form
- Adverse events form

